### Supportive maternal continuous efficacy endpoints

- Last planned average PPG prior to delivery after GW 16
  - Average of three main meals
- Last planned FPG prior to delivery after GW 16

The above continuous endpoints will be analysed using similar modelling approaches as for the primary endpoint with the associated baseline response as a covariate.

## 17.4.2 Safety endpoints

### 17.4.2.1 Classification of Hypoglycaemia in subjects

Treatment emergent: hypoglycaemic episodes will be defined as treatment emergent if the onset of the episode occurs on or after the first day of trial product administration, and no later than 7 days from the last day on trial product.

Nocturnal hypoglycaemic episodes: episodes occurring between 00:01 and 05.59 both inclusive.

Hypoglycaemic episodes are classified according to the Novo Nordisk classification of hypoglycaemia (see [Figure 17-1](#)) and the ADA classification of hypoglycaemia (see [Figure 17-2](#)).

### Novo Nordisk classification of hypoglycaemia

In normal physiology, symptoms of hypoglycaemia occur below a plasma glucose level of 3.1 mmol/L (56 mg/dL). Therefore, Novo Nordisk has included hypoglycaemia with plasma glucose levels below this cut-off point in the definition of BG confirmed hypoglycaemia.

Protocol  
 Trial ID: NN1250-4300  
 UTN: U1111-1191-3018  
 EudraCT no.: 2017-000048-17

[figure not shown]
CONFIDENTIAL

Date: 17 December 2020  
 Version: 4.0  
 Status: Final  
 Page: 91 of 110

Novo Nordisk

Novo Nordisk uses the following classification in addition to the ADA classification:

- Severe hypoglycaemia according to the ADA classification.
- Symptomatic BG confirmed hypoglycaemia: An episode that is BG confirmed by plasma glucose value <3.1 mmol/L (56 mg/dL) **with** symptoms consistent with hypoglycaemia.
- Asymptomatic BG confirmed hypoglycaemia: An episode that is BG confirmed by plasma glucose value <3.1 mmol/L (56 mg/dL) **without** symptoms consistent with hypoglycaemia.
- Severe or BG confirmed symptomatic hypoglycaemia: An episode that is severe according to the ADA classification or BG confirmed by a plasma glucose value <3.1 mmol/L (56 mg/dL) **with** symptoms consistent with hypoglycaemia.
- BG confirmed hypoglycaemia: An episode that is BG confirmed by a plasma glucose value <3.1 mmol/L (56 mg/dL) **with** or **without** symptoms consistent with hypoglycaemia.
- Severe or BG confirmed hypoglycaemia: An episode that is severe according to the ADA classification or BG confirmed by a plasma glucose value <3.1 mmol/L (56 mg/dL) **with** or **without** symptoms consistent with hypoglycaemia.

Note: Glucose measurements are performed with capillary blood calibrated to plasma equivalent glucose values

BG: blood glucose PG: plasma glucose SMPG: Self-measured plasma glucose

Figure 17–1 Novo Nordisk classification of hypoglycaemia

### ADA classification of hypoglycaemia

- Severe hypoglycaemia: An episode requiring assistance of another person to actively administer carbohydrate, glucagon, or take other corrective actions. Plasma glucose concentrations may not be available during an event, but neurological recovery following the return of plasma glucose to normal is considered sufficient evidence that the event was induced by a low plasma glucose concentration.

[figure not shown]
Protocol  
 Trial ID: NN1250-4300  
 UTN: U1111-1191-3018  
 EudraCT no.: 2017-000048-17

CONFIDENTIAL

Date: 17 December 2020  
 Version: 4.0  
 Status: Final  
 Page: 92 of 110

Novo Nordisk

- Asymptomatic hypoglycaemia: An episode not accompanied by typical symptoms of hypoglycaemia, but with a measured plasma glucose concentration  $\leq 3.9$  mmol/L (70 mg/dL).
- Documented symptomatic hypoglycaemia: An episode during which typical symptoms of hypoglycaemia are accompanied by a measured plasma glucose concentration  $\leq 3.9$  mmol/L (70 mg/dL).
- Pseudo-hypoglycaemia: An episode during which the person with diabetes reports any of the typical symptoms of hypoglycaemia with a measured plasma glucose concentration  $> 3.9$  mmol/L (70 mg/dL) but approaching that level.
- Probable symptomatic hypoglycaemia: An episode during which symptoms of hypoglycaemia are not accompanied by a plasma glucose determination but that was presumably caused by a plasma glucose concentration  $\leq 3.9$  mmol/L (70 mg/dL).

Note: Glucose measurements are performed with capillary blood calibrated to plasma equivalent glucose values

PG: plasma glucose SMPG: Self-measured plasma glucose

**Figure 17–2 ADA classification of hypoglycaemia**

### Hypoglycaemia during the pregnancy period

Data on treatment-emergent hypoglycaemic episodes with onset during the pregnancy period are presented in terms of the number of subjects with at least one event (N), the percentage of subjects with at least one event (%), the number of events (E) and the event rate per 100 years of exposure (R).

Protocol  
Trial ID: NN1250-4300  
UTN: U1111-1191-3018  
EudraCT no.: 2017-000048-17

~~CONFIDENTIAL~~

Date: 17 December 2020  
Version: 4.0  
Status: Final  
Page: 93 of 110

**Novo Nordisk**

Summaries will be based on SASpregnant and will display:

- Number of severe or BG confirmed symptomatic hypoglycaemic episodes
- Number of nocturnal, severe or BG confirmed symptomatic hypoglycaemic episodes
- Number of severe hypoglycaemic episodes
- Number of hypoglycaemic episodes according to ADA definition

Data on all hypoglycaemic episodes with onset during the pregnancy period will be presented similarly.

#### **Hypoglycaemia during the in-trial period, the pre-pregnancy period and the post-pregnancy period**

Treatment emergent hypoglycaemic episodes with onset in the pre-pregnancy period, the post-pregnancy period as well as all treatment emergent hypoglycaemic episodes during the in-trial period will be summarised similarly as described for the hypoglycaemic events during the pregnancy period.

Data on all hypoglycaemic episodes within each of the three periods will be presented similarly.

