**Novo Nordisk**

The **pregnancy period** is defined as the period from first day of pregnancy (date of conception corresponding to the first day in GW 2) or randomisation (whichever comes last) to the date of delivery. The first day of pregnancy is based on the estimated gestational age from the US scan made before or at randomisation (visit 2) for subjects randomised pregnant and before or at visit 55 for subjects randomised non-pregnant and becoming pregnant in the conception period of the trial. For subjects with delivery prior to the US scan the first day of pregnancy is determined by the investigator based on the estimated gestational age at the time of delivery.

The **pre-pregnancy period** is defined for subjects randomised as non-pregnant. The period starts at randomisation (visit 2). Two different end-dates will be defined. For subjects who become pregnant the period ends at the day prior to first day of pregnancy. For subjects who do not become pregnant during the trial, the period ends at the same time as the in-trial period.

The **post-pregnancy period** starts the day after the delivery and ends at the same time as the in-trial period.

These definitions form the basis for combinations of periods. The **on-treatment pregnancy period** is e.g. the intersection between the on-treatment period and the pregnancy period.

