**Table 5-6 Analysis of supportive maternal safety endpoint**

Endpoint	Endpoint type	Analysis method	Analysis set	Further information
Number of hypoglycaemic episodes by classification	Discrete	Summary by treatment arm separately for randomised pregnant and randomised non-pregnant *	SAS pregnant	Refer to protocol section 17.4.2.1  For completeness we have also presented a summary based on full analysis set (in-trial data)
Development of sight-threatening retinopathy from treatment baseline as well as from pregnancy baseline to the end of treatment visit	Categorical	Summary by treatment arm separately for randomised pregnant and randomised non-pregnant (Shift table)	SAS pregnant	Refer to protocol section 17.4.2.2
Pre-eclampsia	Discrete	Summary by treatment arm separately for randomised pregnant and randomised non-pregnant *	SAS pregnant	Refer to protocol section 17.4.2.2
Mode of delivery	Discrete	Summary by treatment arm separately for randomised pregnant and randomised non-pregnant	SAS pregnant	Refer to protocol section 17.4.2.2
Change in body weight from pregnancy baseline to last	Continuous	Summary by treatment arm and visits separately for randomised pregnant	SAS pregnant	Refer to protocol section 17.4.2.2

Statistical Analysis Plan  
 Trial ID: NN1250-4300  
 UTN: U1111-1191-3018  
 EudraCT No: 2017-000048-17

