**Novo Nordisk**

planned visit before delivery		and randomised non-pregnant		For completeness we have also presented a summary of change from treatment baseline for randomised non-pregnant subjects.
Number of adverse events during pregnancy period.	Discrete	Summary by treatment arm*	SAS pregnant	

\*The number of subjects with at least one event (N), the percentage of subjects with at least one event (%), the number of events (E) and the event rate per 100 years of exposure (R) will be presented.

Endpoint	Analysis method	Analysis set	Further information
Number of adverse events during pregnancy period.	Summary by treatment arm*	SAS pregnant	
 
• Summaries of TEAEs and of serious TEAEs will be presented as an overview including all TEAEs, serious TEAEs, TEAEs by severity, TEAEs by relation to treatment and TEAEs leading to treatment discontinuation or withdrawal.
 
• Summary tables based on system organ class and preferred terms are made for:               
 
• All TEAEs
 
• Serious TEAEs
 
• TEAEs possibly or probably related to trial product
 
• Severe, moderate and mild TEAEs
 
• TEAEs with preferred term that are experienced by at least 5% of
 
 
 

Statistical Analysis Plan  
 Trial ID: NN1250-4300  
 UTN: U1111-1191-3018  
 EudraCT No: 2017-000048-17

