### 6.2.1 Maternal safety endpoints

#### Pre-eclampsia

For Pre-eclampsia summary, the number and percentage of subjects experiencing PE as well as the event rate per 100 years of observation will be displayed.

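### All-episode and in-trial hypoglycaemia rates are given per 100 years of exposure although the episodes counted include time after trial insulin has stopped; the denominator should be observation time within the period

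*Protocol*

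**What the plan says.** Protocol 17.4.2.1 summarises treatment-emergent episodes in the pregnancy period by number and percentage of women with an episode, number of episodes, and "the event rate per 100 years of exposure". It then extends this layout in two steps. For the pregnancy period: "Data on all hypoglycaemic episodes with onset during the pregnancy period will be presented similarly". For the in-trial, pre-pregnancy and post-pregnancy periods: "Data on all hypoglycaemic episodes within each of the three periods will be presented similarly". No other denominator is named.

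The post-pregnancy period (Protocol 17.2) "starts the day after the delivery and ends at the same time as the in-trial period", and the in-trial period ends at V92. Episodes are reported from randomisation to the end of the trial (Protocol 8.5.16.3).

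The footnote to SAP Table 5-6, flagged in the hypoglycaemia and pre-eclampsia rows, repeats that "the event rate per 100 years of exposure (R) will be presented". The hypoglycaemia row also mentions an additional summary of in-trial data on the full analysis set. SAP 6.2.1, which lists departures from the protocol, changes the denominator for one endpoint only, pre-eclampsia: "the event rate per 100 years of observation will be displayed".

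**The concern.** A rate is interpretable only when events and person-time come from the same window. Here the all-episode counts include time after trial insulin has stopped, while the only denominator named is exposure. Three things point to exposure meaning time on trial product:

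- The safety analysis sets (Protocol 17.2) are defined by being exposed to at least one dose of trial product.
- The definition of treatment-emergent adverse events (Protocol 17.4.2.2) speaks of exposure to randomised treatment.
- The sponsor recorded the move from exposure to observation for pre-eclampsia as a change to the planned analysis, so it regards the two terms as different.

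On that reading, each completer contributes 30 days of episodes but no denominator time after end of treatment. A post-pregnancy rate would then look higher than a pregnancy rate simply because of how it was divided. Maternal hypoglycaemia is a key safety topic, and Protocol 5.2 justifies the treat-to-target design as allowing a valid comparison of safety endpoints, so the absolute rates will be read closely.

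**Working it through.** **Inputs.** End of treatment is 28 days after delivery (Protocol 8.4.3). V92 is 30 days after end of treatment (8.5.3). The treatment-emergent window runs to 7 days after the last day on trial product (17.4.2.1). The protocol expects fewer than 12% to discontinue treatment (Section 17, missing data considerations).

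**The plan's own figure.** 28 + 30 = 58 days from delivery to V92, which matches the 58 days stated in Protocol 8.3.3.

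**Post-pregnancy, all episodes, completer.** Let r be the off-drug episode rate divided by the on-drug rate. Episodes per exposure year, relative to the on-drug rate, are 1 + r × 30/28.

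| r | Factor |
|---|---|
| 0 | 1.00 |
| 0.5 | 1.54 |
| 1 | 58/28 = 2.07 |
| 1.5 | 2.61 |

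At r = 1 the on-drug rate equals the rate per observed year, so 2.07 is the inflation against observed time. If V90 falls 25 to 31 days after delivery and V92 30 to 35 days after V90, the r = 1 factor ranges from (31 + 30)/31 = 1.97 to (25 + 35)/25 = 2.40.

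**In-trial, all episodes, completer, r = 1.** With T on-treatment days, the factor is (T + 30)/T. Delivery at GW 36-40 and, for women randomised non-pregnant, conception at weeks 4-52 are assumptions. Randomisation of pregnant women at GW 8 to 13 + 6 days is from the protocol.

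- Randomised at GW 8, delivery at GW 40: T = 280 − 56 + 28 = 252; 282/252 = 1.12.
- Randomised at GW 11, delivery at GW 38: T = 189 + 28 = 217; 247/217 = 1.14.
- Randomised at GW 13 + 6 days, delivery at GW 36: T = 252 − 97 + 28 = 183; 213/183 = 1.16.
- Randomised non-pregnant, conception (GW 2) at week 52, delivery at GW 40: T = 364 + 266 + 28 = 658; 688/658 = 1.05.
- Randomised non-pregnant, conception at week 4, delivery at GW 36: T = 28 + 238 + 28 = 294; 324/294 = 1.10.

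The in-trial inflation is therefore about 5-16%.

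**Pregnancy period, all episodes.** Completers stay on trial insulin past delivery, so only discontinuers matter. If a fraction f stop and spend a share s of the period off drug, the factor at r = 1 is 1/(1 − f × s). With f = 0.06 and s = 0.25 it is 1/0.985 = 1.02; with f = 0.12 and s = 0.75 it is 1/0.91 = 1.10. The value 0.12 is the protocol's upper expectation; 0.06 and the values of s are assumptions.

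**Treatment-emergent episodes.** After delivery the count can cover 28 + 7 = 35 days against 28 days of exposure: 35/28 = 1.25 at r = 1. For a completer in the pregnancy period the 7-day window falls after delivery, so the factor is 1.00.

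**Footnote against 6.2.1.** The pre-eclampsia row of Table 5-6 carries the exposure footnote, while 6.2.1 says observation for the same endpoint. Both cannot apply.

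**The case against.** The strongest reply is that neither document defines years of exposure for these rates, and that presenting data similarly may mean the same layout with person-time matched to each period. The pre-eclampsia row supports this: the footnote says exposure where 6.2.1 says observation, so the footnote word is not a firm definition. This stands, and it makes the inflation conditional. It does not remove the need to act. If exposure already meant period time, the 6.2.1 change would do nothing, and two programmers could still produce different tables.

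A reader might infer that the post-pregnancy rate is simply doubled. The documents do not support that without the condition r = 1. Daily two-point glucose profiles are required only until end of treatment (Protocol 8.5.14), so fewer asymptomatic low values may be found afterwards, which would pull r below 1.

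A reader might also infer that the key endpoint or the arm comparison is distorted. The listed endpoint counts episodes in the pregnancy period, when completers are still on trial insulin. The 30 days of off-drug follow-up are planned equally in both arms, so at similar r the inflation largely cancels. A false between-arm ratio requires different discontinuation by arm, for which the documents give no figures; their 15% and 10% refer to women randomised non-pregnant and pregnant. Even an assumed 15% against 5%, all stopping halfway through the period, gives only (1/0.925)/(1/0.975) = 1.05.

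Finally, a reader might take the full-analysis-set summary in Table 5-6 to be footnoted per exposure year and to include women with no exposure at all. The asterisk sits in the analysis-method cell, not on that summary, whose denominator is simply unstated.

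**Conclusion.** The concern holds in a limited form. Taken at its plain meaning, the stated denominator does not match the all-episode counts. If exposure is on-treatment time, the completer's all-episode post-pregnancy rate is 2.07 times the rate per observed year when r = 1, with a factor of 1.54 when r = 0.5. The in-trial inflation of about 5-16% and the all-episode pregnancy-period inflation of about 2-10% rest on the r = 1, timing and discontinuation assumptions given with the calculations. The treatment-emergent pregnancy-period summary is essentially unaffected.

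Absolute rates and comparisons between periods suffer more than the comparison between arms. The tables are descriptive, and the non-inferiority test on HbA1c is not touched. The conflict between the Table 5-6 footnote and SAP 6.2.1 over pre-eclampsia does not depend on any of these assumptions.

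**What to change.** - In the SAP, state that all-episode and in-trial hypoglycaemia summaries, including the one on the full analysis set, are per 100 years of observation within the period, counting in-trial days that fall in that period. This follows what 6.2.1 already does for pre-eclampsia, and 6.2.1 should list it as a further change from Protocol 17.4.2.1.
- Correct the Table 5-6 footnote so that it agrees with 6.2.1 for pre-eclampsia and with the new hypoglycaemia denominator.
- Keep exposure as the denominator for treatment-emergent summaries, define it, and state whether it includes the 7-day window.

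The cost is a short SAP edit and a changed denominator variable in the tables. No new data are needed. The downside is that some reported rates become lower.

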#### **17.4.2.2 Maternal safety endpoints**

##### **Maternal safety endpoints assessed during and after the pregnancy period**

Summaries will be based on SASpregnant unless otherwise specified. Data will be presented for all subjects in SASpregnant, as well as divided according to whether subjects were pregnant at randomisation or not.

##### **Development of sight-threatening retinopathy from treatment baseline as well as from pregnancy baseline to the end of treatment visit**

Sight-threatening retinopathy is defined as proliferative retinopathy or maculopathy. The proportion of subjects developing this between treatment baseline/pregnancy baseline to the end of treatment as well as to the additional end of treatment visit will be summarised by treatment arm.

##### **Pre-eclampsia**

Pre-eclampsia (PE) is defined as new-onset hypertension (blood pressure  $\geq 140$  mmHg systolic or  $\geq 90$  mmHg diastolic, based on at least 2 measurements taken at least 4 hours apart) occurring from GW 20 to delivery and simultaneous proteinuria (defined as  $\geq 300$  mg protein in a 24 hours urine sample, a protein-to-creatinine ratio of  $\geq 300$  mg/g in a urine sample or a urine dipstick protein of 1+) or presence of eclampsia, HELLP syndrome, or other severe organ involvement.

The number and percentage of subjects experiencing PE as well as the event rate per 100 years of exposure (R) will be displayed.

##### **Mode of delivery**

Protocol  
 Trial ID: NN1250-4300  
 UTN: U1111-1191-3018  
 EndraCT no.: 2017-000048-17

~~CONFIDENTIAL~~

Date: 17 December 2020  
 Version: 4.0  
 Status: Final  
 Page: 94 of 110

**Novo Nordisk**

The endpoint will be summarised by treatment arm based on the in trial data. The number and percentage of subjects in each category will be displayed. The endpoint will further be summarised according to the following sub-groups:

- Subjects randomised as pregnant
- Subjects randomised as non-pregnant
- Subjects randomised as non-pregnant and exposed to trial drug at some point during the pregnancy period
- Subjects randomised as non-pregnant and not exposed to trial drug during the pregnancy period

**Change in body weight from pregnancy baseline to last planned visit before delivery**

Change in body weight from pregnancy will be summarised by treatment arm and visit for all visits including last planned visit before delivery.

**Adverse events during the pregnancy period**

Adverse events will be coded using the most recent version of the Medical Dictionary for Regulatory Activities (MedDRA) database.

A treatment emergent AE (TEAE) is defined as an event that has onset date on or after the first day of exposure to randomised treatment and no later than 7 days after the last day of randomised treatment. If the event onset date is before the first day of exposure on randomised treatment and increases in severity at some point during the on-treatment period, then this event should also be considered as a TEAE. Major adverse cardiovascular events (MACEs, defined as all cardiovascular deaths, non-fatal myocardial infarctions and non-fatal strokes) are considered treatment-emergent until 30 days after the last day of randomised treatment.

Treatment emergent AEs are summarised descriptively. Data from TEAEs will be displayed in terms of the number of subjects with at least one event (N), the percentage of subjects with at least one event (%), the number of events (E) and the event rate per 100 years of exposure (R).

Adverse events with onset during the pregnancy period are defined as corresponding to the pregnancy period. Number of TEAEs during the pregnancy period will be summarised based on all subjects in SASpregnant.

Summaries of TEAEs and of serious TEAEs will be presented as an overview including all TEAEs, serious TEAEs, TEAEs by severity, TEAEs by relation to treatment and TEAEs leading to treatment discontinuation or withdrawal.

Furthermore, summary tables based on system organ class and preferred terms are made for:

- All TEAEs
- Serious TEAEs
- TEAEs possibly or probably related to trial product

Protocol  
 Trial ID: NN1250-4300  
 UTN: U1111-1191-3018  
 EudraCT no.: 2017-000048-17

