###### Supportive maternal safety endpoints

The pregnancy period is defined as the period from the first day of pregnancy (date of conception) or randomisation (whichever comes last) to the date of delivery. The first day of pregnancy is calculated from the estimated gestational age from the ultrasound scan made before or at randomisation (visit 2) for subjects randomised pregnant and before or at visit 55 for subjects randomised non-pregnant and becoming pregnant in the conception period of the trial. For subjects with delivery prior to the ultrasound scan, the first day of pregnancy is determined by the investigator based on the estimated gestational age at time of delivery.

Two different baselines will be applied; a treatment baseline and a pregnancy baseline. For all subjects the treatment baseline is defined as the latest available measurement at or before randomisation (visit 2). For subjects randomised pregnant the pregnancy baseline is derived from the treatment baseline, and the two baseline values will be identical. For subjects randomised non-pregnant and becoming pregnant in the conception period of the trial, the pregnancy baseline corresponds to data from visit 55.

- Number of hypoglycaemic episodes during the pregnancy period (from first day of pregnancy (date of conception) or randomisation (whichever comes last) to delivery)
- Development of sight-threatening retinopathy defined as proliferative retinopathy or maculopathy from treatment baseline as well as from pregnancy baseline to the end of treatment visit (yes/no)
- Number of adverse events during the pregnancy period (from first day of pregnancy (date of conception) or randomisation (whichever comes last) to delivery)
- Pre-eclampsia defined as new-onset hypertension (blood pressure ≥ 140 mmHg systolic or ≥ 90 mmHg diastolic, based on at least 2 measurements taken at least 4 hours apart) occurring from GW 20 to delivery and simultaneous proteinuria (defined as ≥ 300 mg protein in a 24 hours urine sample, a protein-to-creatinine ratio of ≥ 300 mg/g in a urine sample or a urine dipstick protein of 1+) or presence of eclampsia, HELLP syndrome, or other severe organ involvement (yes/no)

Protocol  
Trial ID: NN1250-4300  
UTN: U1111-1191-3018  
EudraCT no.: 2017-000048-17

CONFIDENTIAL

Date: 17 December 2020  
Version: 4.0  
Status: Final  
Page: 27 of 110

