**Novo Nordisk**

- Severe, moderate and mild TEAEs
- TEAEs with preferred term that are experienced by at least 5% of the subjects in any treatment or by at least 5% of all subjects

Summary tables of all SAEs including non-treatment emergent SAEs will be presented including summary tables based on system organ class and preferred terms.

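### The maternal adverse-event endpoint covers all events to delivery, but the specified analysis covers treatment-emergent events only, so later non-serious events have no pregnancy-period table (minor)

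*Protocol*

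**What the plan says.** **Endpoint.** Protocol 4.4 lists "Number of adverse events during the pregnancy period (from first day of pregnancy (date of conception) or randomisation (whichever comes last) to delivery". The protocol summary and SAP 1.1.2.2 define it in the same way. None of the three mentions treatment emergence.

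**Analysis in the protocol.** Section 17.4.2.2 assigns adverse events to the pregnancy period by onset date and then narrows the count: "Number of TEAEs during the pregnancy period will be summarised based on all subjects in" SAS_pregnant. A TEAE must start "no later than 7 days after the last day of randomised treatment". Major adverse cardiovascular events are the exception and "are considered treatment-emergent until 30 days after the last day of randomised treatment". Beyond TEAEs the section adds one item: "Summary tables of all SAEs including non-treatment emergent SAEs will be presented".

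**Analysis in the SAP.** In section 5.4.2.1 the endpoint appears twice. The row in Table 5-6 names adverse events during the pregnancy period, with N, %, E and R, and sets no TEAE limit. The more detailed table that follows begins "Summaries of TEAEs and of serious TEAEs will be presented as an overview including all TEAEs" and lists only TEAE tables plus all SAEs. The text then refers the reader back to protocol 17.4.2.2.

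**Comparison endpoint.** For hypoglycaemia, protocol 17.4.2.1 plans treatment-emergent summaries and then adds: "Data on all hypoglycaemic episodes with onset during the pregnancy period will be presented similarly".

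**The concern.** The endpoint's observation period ends at delivery. The analysis stops counting non-serious events 7 days after the last trial dose. For a woman who stays on treatment the two agree, because treatment runs to 28 days after delivery. For a woman who stops during pregnancy, or before conceiving, they do not.

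The reported count would carry the endpoint's name while answering an on-treatment question. Comparing maternal safety is a secondary objective, the trial is open-label, and protocol 3.1 says degludec had not been tested in a clinical trial with pregnant subjects. A reader will expect the count to be the one defined.

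The data should be available. Protocol 12.2 collects adverse events to V92, and section 8.4.4 asks pregnant women who stop trial product to attend all remaining visits.

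**Working it through.** **1. Which events have no table.** Take an event with onset between conception (or randomisation, if later) and delivery, more than 7 days after the last trial dose.

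- SAE: tabulated, because all SAEs are summarised.
- Hypoglycaemic episode: tabulated, because all pregnancy-period episodes are presented.
- Pre-eclampsia: has its own summary, with a rate per year of observation (SAP 6.2.1).
- MACE: counted as a TEAE up to 30 days.
- Any other non-serious event: meets the endpoint definition, with no pregnancy-period table specified.

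**2. How many women.** Protocol section 17 (missing data, primary estimand) assumes that at most 15% of women randomised non-pregnant and 10% of those randomised pregnant stop treatment, and that about 80% of the pregnant women are randomised pregnant.

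- Weighted rate: 0.20 × 15% + 0.80 × 10% = 11.0%, which agrees with the plan's own statement of less than 12%.
- In the planned numbers (142 randomised pregnant, and 50% of 72 = 36 conceiving): 0.10 × 142 + 0.15 × 36 = 14.2 + 5.4 = 19.6 of 178.
- At the 12% ceiling: 0.12 × 178 = 21.4.

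**3. How much pregnancy-period time.** The documents do not say when women stop, so this step rests on assumptions. Let L be the length of the pregnancy period in weeks. Entry at GW 8 to 14 and delivery at GW 38 (assumed) give L = 24 to 30, midpoint 27. If stopping is uniform over L, the mean share of a discontinuer's period beyond the 7-day tail is (L − 1)² / (2L²).

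- L = 27: 26² / (2 × 27²) = 676 / 1458 = 0.464.
- At 11% discontinuation: 0.11 × 0.464 = 5.1% of all pregnancy-period time.
- At 12%: 0.12 × 0.464 = 5.6%.

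Range at 12% for other stopping times:

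- All stop in the last quarter: about 1%.
- All stop on day 1: 0.12 × 26/27 = 11.6%.

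**4. How much an added table could recover.** The same protocol section supposes that data can be retrieved from half of the women who stop. Carrying that over to adverse events gives 0.055 × 0.464 = 2.6%. Protocol 12.5 asks for some pregnancy information on paper forms after withdrawal of consent, so the figure is approximate.

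**5. Women who stop before conceiving.** A woman randomised non-pregnant who takes one dose, stops, and conceives more than 7 days later is in SAS_pregnant by definition. She counts in the denominator for N and % but cannot contribute a non-serious TEAE with onset in pregnancy (MACE within 30 days excepted). The plan implies about 5 discontinuers among the 36 (15% × 36 = 5.4) at any time, and only some of these would stop before conception.

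**6. Which statistics move.** N, % and E are affected directly. R is per 100 years of exposure, so events and time are cut together. It is less distorted, but it remains an on-treatment rate.

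**The case against.** TEAE summaries are conventional, and the endpoint is supportive and descriptive, so no test depends on it. For at least 88% of women the TEAE window covers the pregnancy period from first dose. SAEs, hypoglycaemia and pre-eclampsia are captured elsewhere. All of this stands and limits the point to a minor one.

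Two textual replies go less far. The Table 5-6 row carries no TEAE limit, so the SAP is ambiguous rather than plainly TEAE-only. Yet the detailed table and the reference back to the protocol both point to TEAEs. Protocol 17.4.2.2 also says that all in-trial adverse events will be summarised, but in the manner already described, which is the TEAE format. Even read broadly, that gives an in-trial total and not the pregnancy-period endpoint.

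A reader might infer more than the documents support:

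- *The arm with more discontinuation will look safer.* Discontinuation is given by pregnancy status at randomisation, not by arm, so the documents supply no arm difference from which to compute a bias. R is also less affected than the counts.
- *The SAP made an undeclared change.* SAP Appendix 2 lists departures from the protocol's planned analyses. The TEAE summary is the protocol's plan, so there was nothing to declare.
- *About 5% of adverse events are lost.* That figure is person-time under an assumed stopping pattern. Part of it belongs to women who leave the trial, and several event classes are reported anyway.
- *Efficacy and safety rest on different footings.* HbA1c also has an on-treatment (secondary) estimand, which pairs with the TEAE tables.

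**Conclusion.** The mismatch between definition and analysis is real: followed as written, the plan leaves part of a defined endpoint without a table. The gap is confined to non-serious adverse events, other than hypoglycaemia and pre-eclampsia, that start after the treatment-emergent window and before delivery.

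Its size is modest. The plan's discontinuation figures are upper limits, and the time-based percentages rest on uniform stopping, delivery at GW 38 and retrieval from half of the discontinuers. None of these timing or retrieval assumptions is a documented fact about adverse events. Severity is minor. The reason to act is that the reported count should match the endpoint as defined, and that the plan already presents both versions for hypoglycaemia.

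**What to change.** Add to protocol 17.4.2.2 and SAP 5.4.2.1 one summary of all adverse events with onset in the pregnancy period. It should use in-trial data regardless of discontinuation and show N, %, E and a rate per 100 years of pregnancy-period observation. Name it as the analysis of the endpoint as defined, and state the analysis set. Keep the TEAE tables as the on-treatment version, as is done for hypoglycaemia.

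The cost is one further set of descriptive tables from data already collected, and a wording change in both documents.
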